			
 - Consult nephrologist and consider renal biopsy if clinically indicated. - Start prednisone 0.5 – 1 mg/kg/day if other causes are ruled out - If event is persistent beyond 5 days or worsens, increase to prednisone up to 2 mg/kg/day PO or IV equivalent. - If event is not responsive within 5 days or worsens despite prednisone at 1 to 2 mg/kg/day PO or IV equivalent, consider additional workup. When event returns to baseline, resume study drug/study regimen and routine serum creatinine monitoring per study protocol.
	Grade 3 or 4	Permanently discontinue study drug/study regimen.	
For Grade 3 or 4
 
 - Carefully monitor serum creatinine daily. - Follow urine protein/creatinine ratio every 3-7 days - Consult nephrologist and consider renal biopsy if clinically indicated. - Promptly start prednisone 1 to 2 mg/kg/day PO or IV equivalent. - If event is not responsive within 3 to 5 days of steroids or worsens despite prednisone at 1 to 2 mg/kg/day PO or IV equivalent, consider additional workup and prompt treatment with an immunosuppressant
Rash or Dermatitis (Including Pemphigoid)	Any Grade (Refer to NCI CTCAE applicable version in study protocol for definition of severity/grade depending on type of skin rash)	General Guidance	
For Any Grade
 
 - Patients should be thoroughly evaluated to rule out any alternative etiology. - Monitor for signs and symptoms of dermatitis (rash and pruritus). 
HOLD STUDY DRUG IF GRADE 3 PEMPFIGOID OR SEVERE CUTANEOUS ADVERSE REACTION (SCAR)¹ IS SUSPECTED.
 
 - PERMANENTLY DISCONTINUE STUDY DRUG IF SCAR OR GRADE 3 PEMPFIGOID IS CONFIRMED.

	Grade 1	No dose modifications.	For Grade 1 
 – Consider symptomatic treatment, including oral antipruritics (e.g., diphenhydramine or hydroxyzine) and topical therapy (e.g., emollient, lotion, or institutional standard).

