	Grade 2	For persistent (>1 week) Grade 2 events, hold scheduled study drug/study regimen until resolution to Grade ≤1 or baseline. 
 • If toxicity improves to Grade ≤1 or baseline, then resume drug/study regimen after completion of steroid taper (<10 mg prednisone, or equivalent). 	For Grade 2 
 – Consider dermatology consult and skin biopsy, as indicated. – Consider symptomatic treatment, including oral antipruritics (e.g., diphenhydramine or hydroxyzine) and topical therapy – Consider moderate-strength topical steroid. – If no improvement of rash/skin lesions occurs within 1 week or is worsening despite symptomatic treatment and/or use of moderate strength topical steroid, consider discussing with Clinical Study Lead, as needed, and promptly start systemic steroids such as prednisone 1 to 2 mg/kg/day PO or IV equivalent.
	Grade 3	For Grade 3 
 – Hold study drug/study regimen until resolution to Grade ≤1 or baseline. – If toxicity improves to Grade ≤1 or baseline, then resume drug/study regimen after completion of steroid taper (<10 mg prednisone, or equivalent). 	For Grade 3 
 – Reconsult a dermatologist. Consider skin biopsy (preferably more than 1) as clinically feasible. – Promptly initiate empiric IV methylprednisolone 1 to 2 mg/kg/day or equivalent. – Consider hospitalization. – Monitor the extent of rash [Rule of Nines]. – Consider, as necessary, discussing with Clinical Study Lead.
	Grade 4	For Grade 4 Permanently discontinue study drug/study regimen.	For Grade 4 
 – Reconsult a dermatologist. Consider skin biopsy (preferably more than 1) as clinically feasible. – Promptly initiate empiric IV methylprednisolone 1 to 2 mg/kg/day or equivalent. – Consider hospitalization. – Monitor the extent of rash [Rule of Nines]. Consider, as necessary, discussing with Clinical Stud

			Study Lead.

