			
 - Consider discussing with the Clinical Study Lead, as needed. - Promptly start IV methylprednisolone 2 to 4 mg/kg/day systemic steroids along with receiving input from Neurology consultant. - If after start of IV methylprednisolone at 2 to 4 mg/kg/day there is no improvement within 2 to 3 days, consider starting another immunosuppressive therapy such as a TNF inhibitor (e.g., infliximab at 5 mg/kg IV, may be repeated at 2 and 6 weeks after initial dose at the discretion of the treating provider or relevant practice guidelines). Caution: It is important to rule out sepsis and refer to infliximab label for general guidance before using infliximab.
--	--	--	--

¹ SCAR terms include Stevens-Johnson Syndrome (SJS), Toxic Epidermal Necrolysis (TEN), Erythema Multiforme, Acute Generalized Exanthematous Pustulosis, Drug Reaction with Eosinophilia and Systemic Symptoms (DRESS) and Drug-induced hypersensitivity syndrome.

Other–Immune-Mediated Reactions

Severity Grade of the Event (Refer to NCI CTCAE applicable version in study protocol for defining the CTCAE grade/severity)	Dose Modifications	Toxicity Management
Any Grade	Note: It is possible that events with an inflammatory or immune mediated mechanism could occur in nearly all organs, some of them are not noted specifically in these guidelines (e.g. immune thrombocytopenia, haemolytic anaemia, uveitis, vasculitis).	
 – Patients should be thoroughly evaluated to rule out any alternative etiology (e.g., disease progression, other medications, or infections). – The Clinical Study Lead may be contacted for immune-mediated reactions not listed in the “specific immune-mediated reactions” section – Consultation with relevant specialist – Treat accordingly, as per institutional standard.
Grade 1	No dose modifications.	Monitor as clinically indicated

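### In Appendix A, the Grade 3 rash dose cell directs restart after improvement without excepting confirmed Grade 3 pemphigoid or SCAR, which the Any Grade text of the same row stops permanently; the Grade 2 cell has this conflict for SCAR only

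*Combined protocol and SAP*

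**What the plan says.** Three parts of Appendix A bear on this.

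- **Any Grade entry of the Rash or Dermatitis row.** The row heading names pemphigoid as included. The Dose Modifications cell carries only a general-guidance label. The instructions on study drug are in the Toxicity Management column. On suspicion: "HOLD STUDY DRUG IF GRADE 3 PEMPFIGOID OR SEVERE CUTANEOUS ADVERSE REACTION (SCAR)¹ IS SUSPECTED". On confirmation: "PERMANENTLY DISCONTINUE STUDY DRUG IF SCAR OR GRADE 3 PEMPFIGOID IS CONFIRMED". The pemphigoid limb is limited to Grade 3; the SCAR limb has no grade limit.
- **Graded Dose Modifications cells of the same row.** Grade 3: "Hold study drug/study regimen until resolution to Grade ≤1 or baseline", followed by "If toxicity improves to Grade ≤1 or baseline, then resume drug/study regimen after completion of steroid taper (<10 mg prednisone, or equivalent". Grade 2: "For persistent (>1 week) Grade 2 events, hold scheduled study drug/study regimen until resolution to Grade ≤1 or baseline", followed by the same restart sentence. Neither cell mentions pemphigoid or SCAR or refers back to the Any Grade entry. Grade 4 is a permanent stop.
- **Footnote 1.** SCAR is defined by a list of diagnoses with no grade threshold: "SCAR terms include Stevens-Johnson Syndrome (SJS), Toxic Epidermal Necrolysis (TEN), Erythema Multiforme, Acute Generalized Exanthematous Pustulosis", and further conditions.

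**The concern.** A table with separate columns for dose modification and for toxicity management invites a site to take its dosing decision from the first of these. In this row that column leads to restart once the event has improved and steroids are tapered. The permanent stop for the most serious diagnoses appears only in the other column, in the Any Grade entry. For a confirmed Grade 3 pemphigoid or SCAR, both cannot be followed.

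What is at stake is mainly patient safety: whether a patient with a confirmed severe skin reaction is re-exposed to durvalumab. The event type is foreseen, since Section 3.2 lists rash or dermatitis including pemphigoid among the drug's risks and Section 9.1.3 lists rash or dermatitis as an adverse event of special interest. A lesser consequence is that sites could handle the same event differently, so that the reason for stopping treatment would not reflect a single trial rule.

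**Working it through.** The plan states no figure on this point, so the check is a comparison of the cells, event by event.

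| Event | Any Grade text | Graded dose cell | Compatible? |
|---|---|---|---|
| Pemphigoid, Grade 3, confirmed | Permanent stop | Hold, then resume | No |
| SCAR graded 3, confirmed | Permanent stop | Hold, then resume | No |
| SCAR, if graded 2, confirmed | Permanent stop | Hold only if longer than 1 week, then resume | No |
| SCAR, if graded 2, suspected | Hold | No hold until longer than 1 week | No, until the event has lasted over a week |
| Pemphigoid, Grade 2 | No specific rule | Hold only if longer than 1 week, then resume | Yes |
| SCAR or pemphigoid, Grade 4 | Stop for confirmed SCAR; silent on Grade 4 pemphigoid | Permanent stop | Yes |

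The first line needs no outside source: pemphigoid is in the row by its heading, and the Any Grade text names Grade 3. The lines on SCAR at Grade 2 need a SCAR event to be graded 2. The row refers grading to CTCAE, which is not among the documents, and footnote 1 assigns no grades.

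Next, does anything elsewhere settle the matter?

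- The general considerations opening Appendix A withhold drug for Grade 3 immune-mediated events and stop it permanently for Grade 4, for recurrent Grade 3 needing systemic immunosuppression, or when steroids cannot be reduced within 12 weeks. For a first Grade 3 event this agrees with the restart cell, not with the stop.
- Section 7.3.1 allows restart once the event has recovered to Grade 1 or lower or there is no safety risk. It has no rule for skin events.
- Section 6.2 withdraws a subject whose drug-related interruption exceeds 4 consecutive weeks, and Section 7.3.1 discontinues treatment for a 4-week delay. These could make the restart cell unreachable in practice, so they need a check.

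Inputs for that check: dosing every 4 weeks, so the next dose is due on day 28 (Section 7.2); a steroid taper of at least 28 days after improvement to Grade 1 or lower (Appendix A, general considerations). Assume that delay is counted from the missed scheduled dose. With onset s days after the last dose and r days to improvement, and the taper at its 28-day minimum:

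- earliest restart day = s + r + 28
- delay = (s + r + 28) − 28 = s + r

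Restart stays inside the limit in Section 7.3.1 when s + r is below 28. An event just after a dose that improves in a week (s = 0, r = 7) allows restart on day 35, a delay of 7 days. An event starting on day 21 with the same course gives a delay of 28 days, and treatment is discontinued. The limits therefore close the restart path for some patients and leave it open for others. If the interruption were instead counted from onset, the first example would run to 35 days, beyond the 28 allowed by Section 6.2. The documents do not say which count applies.

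**The case against.** The strongest answer is that the exception already exists. The instruction is in the Any Grade entry, in capitals, and names specific diagnoses; a specific rule for all grades naturally qualifies the general rash cells below it. The Diarrhea/Colitis row is built the same way: its permanent stop for intestinal perforation is in the Any Grade Toxicity Management text, while the Grade 2 cell and the Grade 3 monotherapy instruction allow resumption without excepting perforation. Few would read those as permitting restart after a perforation.

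This stands as the likelier intent. It does not remove the conflict, because no sentence gives the Any Grade text priority. Nor is its placement the table's settled convention. The hepatitis row puts its Hy's law stop in a graded dose cell, the myositis row puts its respiratory-insufficiency stop in the Grade 2 and Grade 3 dose cells, and the myocarditis row puts its biopsy-proven stop in the Any Grade dose cell. A reader may fairly expect a dosing exception in the dosing column.

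Appendix A also describes itself as a recommendation, and Sections 6.2 and 7.3.1 leave the investigator room to delay or withdraw. Both are true, but neither reconciles two opposite recommendations.

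Some stronger readings do not hold:

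- A reader might infer that restart after any confirmed pemphigoid contradicts the row. The stop names only Grade 3 pemphigoid.
- A reader might infer that SCAR events certainly fall in the Grade 2 cell, or in the Grade 1 cell with its instruction to leave dosing unchanged. A list without a grade threshold does not show that these reactions are graded that low.
- A reader might infer that a site would go on dosing through the first week of a suspected Grade 2 SCAR. With 4-weekly dosing, one week is 7/28, a quarter of the cycle, so it usually contains no scheduled dose.
- A reader might want a probability of harm in the 33 patients. The documents give no incidence. The chance of any such event would also overstate the harm, which requires confirmation, improvement, escape from the 4-week limits, and a site that disregards the Any Grade text.

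**Conclusion.** The point holds in a limited form. The Grade 3 dose cell directs restart without excepting confirmed Grade 3 pemphigoid or SCAR, for which the Any Grade text of the same row requires a permanent stop. The Grade 2 cell has the same conflict for SCAR only, conditional on a SCAR event being graded 2.

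It is best described as a missing exception or cross-reference, made worse because the two instructions sit in different columns. The number of patients affected cannot be estimated from the documents and may be none. For a patient who is affected, the instructions are opposite and the consequence is serious, so it should be corrected. The objective response rate, the two-stage design and the sample size do not depend on it.

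The conclusion rests on the wording of the cells. That restart is reachable rests on the assumption that delay is counted from the missed dose. No view is taken on which clinical rule is right.

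**What to change.** The sponsor should reconcile the Any Grade text of the Rash or Dermatitis row with the graded cells below it. The Dose Modifications column should:

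- give one consistent instruction for suspected SCAR, for confirmed SCAR, and for suspected and confirmed Grade 3 pemphigoid;
- say whether the instruction for SCAR depends on grade;
- say whether the Grade 2 and Grade 3 cells apply only to other rash.

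Which instruction is adopted is a clinical decision for the sponsor. The cost is wording in Appendix A and the usual amendment and notice to sites. No analysis, sample size or data collection changes.

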3.3. FIXED DOSING

A population PK model was developed for durvalumab using monotherapy data from a Phase 1 study (*study 1108; N=292; doses= 0.1 to 10 mg/kg Q2W or 15 mg/kg Q3W; solid tumors*). Population PK analysis indicated only minor impact of body weight (WT) on PK of durvalumab (coefficient of ≤ 0.5). The impact of body WT-based (10 mg/kg Q2W) and

fixed dosing (750 mg Q2W) of durvalumab was evaluated by comparing predicted steady state PK concentrations (5th, median and 95th percentiles) using the population PK model. A fixed dose of 750 mg was selected to approximate 10 mg/kg (based on median body WT of ~75 kg). A total of 1000 patients were simulated using body WT distribution of 40–120 kg. Simulation results demonstrate that body WT-based and fixed dosing regimens yield similar median steady state PK concentrations with slightly less overall between-subject variability with fixed dosing regimen.

Similar findings have been reported by others.²⁴⁻²⁷ Wang and colleagues investigated 12 monoclonal antibodies and found that fixed and body size-based dosing perform similarly, with fixed dosing being better for 7 of 12 antibodies.²⁵ In addition, they investigated 18 therapeutic proteins and peptides and showed that fixed dosing performed better for 12 of 18 in terms of reducing the between-subject variability in pharmacokinetic/pharmacodynamics parameters.²⁶

A fixed dosing approach is preferred by the prescribing community due to ease of use and reduced dosing errors. Given expectation of similar pharmacokinetic exposure and variability, we considered it feasible to switch to fixed dosing regimens. Based on average body WT of 75 kg, a fixed dose of 1500 mg Q4W durvalumab (equivalent to 20 mg/kg Q4W) is included in the current study. Fixed dosing of durvalumab is recommended only for subjects with > 30kg body weight due to endotoxin exposure. Patients with a body weight less than or equal to 30 kg should be dosed using a weight-based dosing schedule (Appendix B).

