Appendix A.

Dosing Modification and Toxicity Management Guidelines (TMGs) for Durvalumab Monotherapy, Durvalumab in Combination with other Products, or Tremelimumab Monotherapy –October 2022

General Considerations Regarding Immune-Mediated Reactions

These guidelines are provided as a recommendation to support investigators in the management of potential immune-mediated adverse events (imAEs).

Immune-mediated events can occur in nearly any organ or tissue, therefore, these guidelines may not include all the possible immune-mediated reactions. Investigators are advised to take into consideration the appropriate practice guidelines and other society guidelines (e.g., National Comprehensive Cancer Network (NCCN), European Society of Medical Oncology (ESMO)) in the management of these events. Refer to the section of the table titled “Other -Immune-Mediated Reactions” for general guidance on imAEs not noted in the “Specific Immune-Mediated Reactions” section.

Early identification and management of imAEs is essential to ensure safe use of the study drug. Monitor patients closely for symptoms and signs that may be clinical manifestations of underlying imAEs. Patients with suspected imAEs should be thoroughly evaluated to rule out any alternative etiologies (e.g., disease progression, concomitant medications, infections). In the absence of a clear alternative etiology, all such events should be managed as if they were immune-mediated. Institute medical management promptly, including specialty consultation as appropriate. In general, withhold study drug/study regimen for severe (Grade 3) imAEs. Permanently discontinue study drug/study regimen for life-threatening (Grade 4) imAEs, recurrent severe (Grade 3) imAEs that require systemic immunosuppressive treatment, or an inability to reduce corticosteroid dose to 10 mg or less of prednisone or equivalent per day within 12 weeks of initiating corticosteroids.

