	Grade 2	Hold study drug/study regimen dose until resolution to Grade ≤ 1 .	
For Grade 2
 
 – Consult a neurologist. – Consider EMG/NCS – Consider discussing with the Clinical Study Lead, as needed. – Observation for additional symptoms or consider initiating prednisone 0.5–1 mg/kg orally – If progression, initiate methylprednisolone 2–4 mg/kg/day and treat as GBS – Sensory neuropathy/neuropathic pain may be managed by appropriate medications (e.g., gabapentin or duloxetine).
	Grade 3 or 4	
For Grade 3 or 4
 
Permanently discontinue study drug/study regimen.
	
For Grade 3 or 4
 
 – Consider discussing with Clinical Study Lead, as needed. – Recommend hospitalization. – Monitor symptoms and consult a neurologist. – Treat per Guillain-Barré Syndrome recommendations

Guillain-Barré Syndrome (GBS)		General Guidance	
 - Recommend hospitalization - Obtain neurology consult - Obtain MRI of spine to rule out compression lesion - Obtain lumbar puncture - Antibody tests for GBS variants - Pulmonary function tests - Obtain electromyography (EMG) and nerve conduction studies - Frequently monitor pulmonary function tests and neurologic evaluations - Monitor for concurrent autonomic dysfunction - Initiate medication as needed for neuropathic pain
	Grade 2-4	Grade 2-4 Permanently discontinue	Start IVIG or plasmapheresis in addition to methylprednisolone 1 gram daily for 5 days, then taper over 4 weeks.
Myasthenia gravis		General Guidance	
 - Obtain neurology consult - Recommend hospitalization - Obtain pulmonary function tests - Obtain labs: ESR, CRP, creatine phosphokinase (CPK), aldolase and anti-striational antibodies - Consider cardiac exam, ECG, troponin, transthoracic echocardiogram for possible concomitant myocarditis - Obtain electromyography (EMG) and nerve conduction studies - Consider MRI of brain/spine to rule out CNS involvement by disease - Avoid medications that might exacerbate MG (e.g. beta blockers, some antibiotics, IV magnesium)
	Grade 2	Permanently discontinue	
 - Consider pyridostigmine 30mg three times daily and gradually increase based on symptoms (max dose 120mg four times daily) - Consider starting low dose prednisone 20mg daily and increase every 3-5 days. (Target dose 1mg/kg/day. Max dose 100mg daily)

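### In Appendix A, the bullet for a progressing Grade 2 peripheral neuropathy gives one methylprednisolone dose and refers to a Guillain-Barré row with another that does not overlap it; the durvalumab action is also unclear on one reading.

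*Combined protocol and SAP*

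**What the plan says.** The text is in the nervous-system part of the Appendix A table, in adjoining rows.

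- **Peripheral neuropathy, Grade 2, dose modification:** "Hold study drug/study regimen dose until resolution to Grade" 1 or lower. The cell says nothing about a case that worsens.
- **Peripheral neuropathy, Grade 2, toxicity management:** consult a neurologist, then observe or consider low-dose oral prednisone. On worsening: "If progression, initiate methylprednisolone 2–4 mg/kg/day and treat as GBS".
- **Peripheral neuropathy, Grade 3 or 4:** stop durvalumab permanently and "Treat per Guillain-Barré Syndrome recommendations". This row gives no mg/kg dose of its own.
- **GBS, dose modification:** "Grade 2-4 Permanently discontinue".
- **GBS, Grades 2 to 4, toxicity management:** "Start IVIG or plasmapheresis in addition to methylprednisolone 1 gram daily for 5 days, then taper over 4 weeks".

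The opening of the appendix describes its status: "These guidelines are provided as a recommendation to support investigators in the management". Neither that opening nor the protocol body says which row prevails when two apply.

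**The concern.** A single bullet gives a weight-based steroid dose and, joined by a plain conjunction, sends the reader to a row with a fixed dose. A clinician who follows the first half and one who follows the reference would prescribe different amounts for the same event. The GBS row also adds intravenous immunoglobulin (IVIG) or plasmapheresis, which the first half does not mention.

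On one reading the instruction for durvalumab differs as well, between a hold that can end in restart and a permanent stop. Neuropathy and neuromuscular toxicity, with Guillain-Barré as an example, is an adverse event of special interest in section 9.1.3, and safety is a secondary objective. The stake is patient safety first. Second is the comparability between sites of treatment exposure and discontinuation records, should the event occur.

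**Working it through.** The plan states no figure to reproduce. The check converts the two doses to a common unit and then sets the durvalumab instructions side by side.

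**Inputs**
- Grade 2 neuropathy bullet: 2 to 4 mg/kg/day (Appendix A).
- GBS row: 1 g = 1000 mg/day (Appendix A).
- Reference weight: "Based on average body WT of 75 kg" (section 3.3).
- Weight range: "A total of 1000 patients were simulated using body WT distribution of 40–120 kg" (section 3.3). This is a simulation range, used here only to show the spread.

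**Formulas**
- Weight-based dose: 2 × W to 4 × W mg/day.
- Ratio of the fixed dose to it: 1000 / (4W) to 1000 / (2W).

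| Weight W | 2–4 mg/kg/day | Fixed dose | Ratio |
|---|---|---|---|
| 40 kg | 80–160 mg | 1000 mg | 1000/160 = 6.3 to 1000/80 = 12.5 |
| 75 kg | 150–300 mg | 1000 mg | 1000/300 = 3.3 to 1000/150 = 6.7 |
| 120 kg | 240–480 mg | 1000 mg | 1000/480 = 2.1 to 1000/240 = 4.2 |

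The doses would meet only at 1000/4 = 250 kg (upper limit) or 1000/2 = 500 kg (lower limit). No weight in the range removes the difference.

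**Durvalumab action.** Two things are undefined: whether progression means worsening within Grade 2 or a move to Grade 3, and whether the reference to GBS brings in the whole row or only its management column.

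| Progression means | Reference covers | Durvalumab |
|---|---|---|
| Worse, still Grade 2 | Management column only | Held under the neuropathy row; the GBS row would stop it |
| Worse, still Grade 2 | Whole GBS row | Permanent stop |
| Reaches Grade 3 | Either | Permanent stop under both rows |

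The action is therefore in conflict on one combination of readings out of the three. The dose conflict is present on all three, because it lies inside the bullet itself.

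**The case against.** **The bullet may describe a sequence.** The weight-based dose could be a start while the GBS work-up proceeds, with the fixed dose to follow. The Grade 2 encephalitis row has that shape: a mg/kg dose, then 1 g daily to be considered under a stated trigger. But that row names its trigger and the neuropathy bullet names none. A sequence is possible, but the text does not say so. It follows that a several-fold difference in what a given patient receives is a worst case, not a certainty.

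**The hold-or-stop conflict is conditional.** A reader might infer that the two rows always give opposite durvalumab instructions. The documents do not support that: if the event reaches Grade 3, or the whole GBS row applies, the instruction is to stop. This stands.

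**The row may seldom be used.** A reader might infer frequent use from prior oxaliplatin exposure and from exclusion 6, which admits Grade 2 or higher neuropathy case by case. The documents do not support that either. Section 3.2 places neuromuscular toxicity among rarer inflammatory events, and Appendix A asks that other causes, including medications, be ruled out first. The synopsis requires refractoriness to only one of three agents, although section 6.1.1 requires all three. Only 33 patients are planned, and no event rate is given. This stands too, and effects on between-site safety data remain speculative.

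**Safeguards exist.** The appendix is advisory and defers to practice guidelines, and the row calls for a neurologist. Restart is limited by the 4-week rules in sections 6.2 and 7.3.1, by the steroid limit in section 7.7.1 and by the taper of at least 28 days in the appendix. These narrow the scope for re-exposure but do not exclude it, since section 7.3.1 contemplates restart after recovery to Grade 1. Nor do they reconcile the two doses: a recommendation with two incompatible doses does not guide the person who consults it.

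**Conclusion.** The dose conflict holds as a plain inconsistency within the text: 150–300 against 1000 mg/day at 75 kg (3.3- to 6.7-fold), and 2.1- to 12.5-fold over 40–120 kg, with no overlap. It rests only on the wording of two rows and on weights taken from section 3.3.

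The durvalumab conflict holds conditionally, on the assumption that progression stays within Grade 2 and the reference covers the management column alone. The text does not settle either point.

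The consequence is confined to safety management and treatment exposure for an event that should be uncommon. The Simon two-stage design and the response-rate analysis are unaffected. This is an error of wording to be corrected, not a flaw in the trial's design.

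**What to change.** The sponsor should reconcile the Grade 2 peripheral neuropathy row with the GBS row by protocol amendment. The amended text should:

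1. give one steroid instruction for a Grade 2 neuropathy that progresses, either by cross-reference alone or by a stated dose that agrees with the row referred to; if a stepwise course is meant, say so and give the trigger;
2. give one durvalumab action for the same event;
3. define progression as worsening within Grade 2, a move to Grade 3, or both;
4. state which row governs once a patient is managed under the GBS recommendations.

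Which dose and which action are right is for the sponsor and its clinical advisers; none is proposed here.

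The cost is a short change to Appendix A, which the version history shows has been amended several times. Under section 11.6 it also means informing the IRB, judging whether formal approval and a consent revision are needed, and notifying sites. Sample size, endpoints and analyses do not change.
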